Comprehension will be assessed by asking the participant to summarize the study activities or some general open ended questions will be asked like what can you tell me about this study, can you tell me about how long the study may last, etc. The consent process is estimated to take around 30 minutes. Study staff will ensure that the participant has signed and dated the consent form including the HIPAA form. All signed consent forms will be stored in locked file cabinets under respective participant files.

Baseline Assessment

The research staff will then administer the baseline assessment which includes a confirmatory set of screening questions via RedCap. Confirmation of the participant's eligibility will be recorded in RedCap. If a participant is ineligible based on this RedCap assessment, they will be given a \$50 incentive and thanked for their time, and they will

not be considered to have been enrolled in the study at any point (informed consent is asked before this point so that we can use any data generated in published findings). If a participant is eligible, they will also be thanked for coming and given their \$50 incentive payment for their time. Completion of Baseline assessment will be recorded in excel logs.

RANDOMIZATION

Our team will utilize a 1:1 ratio for allocation to the STOMP intervention and Usual Care (UC) conditions. Our study statistician, [name], will use SAS to generate the randomization scheme stratified by whether the participant is on long-term opioid therapy (taking prescribed opioids for at least 3 months) and whether they have chronic multisite pain (pain in at least 3 locations or pain all over). Importantly, the PIs and outcomes assessors will be blinded to intervention vs. comparison allocation. Participants in the intervention and comparison conditions will have full access to all available clinical services at their respective sites.

d) INTERVENTION

The intervention group will receive “treatment as usual” plus the STOMP behavioral intervention. The “treatment as usual” refers to the standard of care that patients receive at the UAB and UNC clinics. This standard of care is for patients to discuss chronic pain with their providers at their discretion. Although highly variable, providers can recommend and prescribe pharmacologic (e.g., opioid and other pain medication), non-pharmacologic (e.g., physical therapy, referral to psychology) approaches for pain. This study will not interfere in any way with usual care.

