Sample Size Calculation. Our primary outcome is the BPI-Total score as described above. Given that 20 participants progress through the study at a time, our total sample size should be divisible by 20. A sample size of 210 will provide 85% power to detect a difference of 1 on a 10 point scale with at standard deviation of 2.4 assuming a two-sample t-test with equal variance. The IMMPACT guidelines suggest that a change of 1 on the BPI is a minimum clinically significant difference. Additionally, the difference we found in our pilot trial was 1 (SD=2.4). Therefore, a sample size of 210 is sufficient to detect this effect size. To become divisible by 20 and allow for 25% dropout (slightly more than in the pilot trial) we will recruit 280 participants. With our anticipated sample size, we will be able to estimate a margin-of-error of 1.5 percentage points for 95% intervals. For secondary outcomes, we can detect an effect size of 0.4, a medium effect, for continuous measures and a difference of proportions between 7.5% and 17% for binary measures, each with 85% power.

Interim & Final Analyses. We will not have any planned interim looks for stopping for efficacy, although safety and tolerability data will be monitored by the study DSMB at each meeting. The final analyses will be conducted once study follow-up is complete, after all data is

cleaned, and once the study database is locked. We anticipate database lock will happen by February 2024 with completion of primary analyses occurring by March of the same year.

Analysis Sets. The full analysis set will be based on an intention-to-treat (ITT) analysis with a per-protocol (PP) sensitivity analyses. The ITT analysis set will comprise all participants who have been randomized to either study arm, regardless of length of follow-up or actual intervention received.

Endpoint and Covariates

Our primary outcome will be the Brief Pain Inventory (BPI)-Total score, a commonly used composite measure of pain severity and the impact of pain on an individual's function. The BPI asks 11 questions about pain severity (pain at its worst, least, average, and right now) and the interference of pain in several aspects of patients' lives (activity, mood, walking ability, work, relations with other people, sleep, and enjoyment of life) on a scale of 0 (no pain/does not interfere) to 10 (pain as bad as you imagine/completely interferes). The BPI-Total score is the average score across all 11 questions.

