There were no covariates included in our models, only time and treatment group indicator. We used linear mixed effects models which do not require adjustment for baseline as a fixed effect as it is included as an outcome. This allows for estimation of treatment effects at all follow-up times that takes into account any baseline differences between groups.

Handling of Missing Values. As a preventive measure, we will make every attempt to document all reasons for missing data. In addition, baseline characteristics will be compared between participants who do and do not withdraw from the study as a way to assess the impact of missing information and attrition. We will also compare the rates of lost-to-follow-up (LTF) between study arms.

Our general assumption will be that missing data is of the Missing at Random (MAR) mechanism. In this case, the use of linear mixed models for the primary analysis will be sufficient in reducing the impact that missing data has on biasing the primary results. Additionally, we will conduct a sensitivity analysis using multiple imputation via chained equations (MICE) to see how robust the overall inferences are.

Statistical Analyses.

The primary outcome – BPI-Total score – and the other secondary outcomes will be assessed as continuous variables. Linear mixed effects models will be performed to test differences between intervention and control conditions at the immediate post intervention and at 3 months. Models will include random effects for participant and therapy group. Therapy group is an identifier of the group of 20 that were randomized to create a STOMP group of 10. Fixed effects will be STOMP indicator, time and STOMP by time interaction. The primary hypothesis will be tested using the least squared means of each group at each time. We will check distributional

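### Randomisation is stratified by long-term opioid therapy and chronic multisite pain, but no model in the SAP includes either factor, and the only reason given concerns the baseline value of the outcome

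*Combined protocol and SAP*

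**What the plan says.** The Randomization text in protocol section III.c has the allocation "stratified by whether the participant is on long-term opioid therapy" and by "whether they have chronic multisite pain (pain in at least 3 locations or pain all over"). Blocking is not described. The SAP's Sample Size Calculation ("Given that 20 participants progress through the study at a time") and its Statistical Analyses section ("Therapy group is an identifier of the group of 20 that were randomized to create a STOMP group of 10") imply that batches of 20 are split 10/10.

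The SAP's Endpoint and Covariates section states: "There were no covariates included in our models, only time and treatment group indicator". It continues: "We used linear mixed effects models which do not require adjustment for baseline as a fixed effect as it is included as an outcome". It adds that differences between the groups at baseline are thereby allowed for.

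The Statistical Analyses section agrees with this: "Fixed effects will be STOMP indicator, time and STOMP by time interaction", with random effects for participant and therapy group. The primary test uses the least-squares means of each arm at each time. The responder model takes the same terms as the primary model. The per-protocol sensitivity analysis adds site, which is not a stated stratification factor. The imputation text names baseline outcome data and is run separately by arm. The strata are not mentioned anywhere in the SAP.

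**The concern.** An analysis should normally reflect the restrictions placed on the randomisation. If allocation is balanced within strata and the strata predict the outcome, the difference between arms varies less than an unadjusted model assumes. The reported standard error is then too wide, the test is conservative, and precision that the design paid for is not used. If the strata turn out not to be balanced, the unadjusted standard error is right, but adjusting would still reduce it.

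The reason in the SAP does not settle this. Treating baseline BPI-Total as the first repeated measure deals with the baseline value of that outcome. It gives no ground for leaving out opioid therapy or multisite pain. At stake is efficiency, not validity: there is no bias and no inflation of the type I error.

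**Working it through.** **Inputs.** From the SAP's Sample Size Calculation: difference 1, SD 2.4, 210 evaluable, 85% power, and "allow for 25% dropout (slightly more than in the pilot trial) we will recruit 280 participants". Alpha is not stated; 5% two-sided is assumed. R², the share of BPI-Total variance explained by the two strata, is not in the documents; 0 to 15% is assumed. The closed form covers one time point and ignores clustering by therapy group.

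**The plan's own figure.** n per arm = 2 × (1.960 + 1.036)² × 2.4² / 1² = 103.4, so 104 per arm and 208 in total, against 210 stated. With 105 per arm, power is 85.5% (normal) or 85.2% (t-test). 210 / 0.75 = 280. The sizing reproduces.

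**Formulas.** The test is the difference in arm means at post-intervention.

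- Reported unadjusted SE = 2.4 × √(2/105) = 0.331.
- Suppose the 280 are exactly balanced within strata and a random fraction d = 0.25 drops out. Balance removes the stratum component of the variance, and dropout puts back a fraction d of it. The actual SE of the unadjusted difference is 0.331 × √(1 − 0.75R²).
- Adjusted SE = 0.331 × √(1 − R²).
- SE excess (reported over actual, unadjusted) = 1/√(1 − 0.75R²) − 1.
- Type I error = 2 × [1 − Φ(1.96 × 0.331 / actual SE)].
- Power without strata = Φ((1 − 1.96 × 0.331) / actual SE). Power with strata = Φ(1 / adjusted SE − 1.96).

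Example at R² = 10%: actual SE = 0.319 and adjusted SE = 0.314. Power without strata is Φ(0.351/0.319) = 86.5%, and with strata Φ(3.18 − 1.96) = 88.9%.

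| R² | SE excess | Type I error | Power without / with strata | Loss, balanced (points) | Loss, no balance within strata (points) |
|---|---|---|---|---|---|
| 0% | 0% | 5.0% | 85.5 / 85.5% | 0 | 0 |
| 2% | 0.8% | 4.8% | 85.7 / 86.2% | 0.5 | 0.7 |
| 5% | 1.9% | 4.57% | 86.0 / 87.2% | 1.3 | 1.7 |
| 10% | 4.0% | 4.16% | 86.5 / 88.9% | 2.5 | 3.4 |
| 15% | 6.1% | 3.75% | 87.0 / 90.6% | 3.6 | 5.0 |

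In the last column the actual unadjusted SE equals the reported 0.331, so the SE excess is 0% and unadjusted power stays at 85.5%. With exact balance and no dropout, the SE excess would be 2.6, 5.4 and 8.5% at R² = 5, 10 and 15%; these are upper bounds.

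**Simulation of the repeated-measures model.** Fixed effects were arm, time and arm by time, with a participant random intercept. Baseline was kept for all 280 and post-intervention for 210. There were 18,000 runs. Assumed: stratum prevalences 30% and 60%, within-person correlation 0.5, stratum effects constant over time. Again there was no clustering. Here SE excess is reported over actual SE for the unadjusted model, relative to the same ratio for the adjusted model.

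| Allocation scheme | SE excess at R² = 5, 10, 15% | Type I error at R² = 5, 10, 15% | Power loss (points) at R² = 2, 5, 10, 15% |
|---|---|---|---|
| Blocks of 4 within strata | 2.1, 4.3, 6.5% | 4.6, 4.3, 3.7% | 0.3, 0.9, 1.7, 2.4 |
| Batches of 20 split 10/10, strata as even as possible | 1.7, 3.7, 5.7% | 4.7, 4.2, 3.9% | 0.3, 0.9, 2.0, 2.6 |
| Batches of 20 split 10/10, strata ignored | −0.2, 0.1, 0.1% | not tabulated (SE correct) | 0.4, 1.1, 2.5, 3.9 |

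**Change contrast.** If the test were the difference between arms in change from baseline, a stratum effect constant over time would cancel. With blocks of 4 and R² = 10%, the reported SE is 0.305 without the strata and 0.304 with them.

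**The case against.** The strongest reply is that this is a matter of efficiency only. The trial was sized on an unadjusted two-sample t-test, so a model without covariates matches the sizing, and unadjusted power stays at about 85% or above. The SAP states its choice openly. All of that stands, and it limits how much weight the point should carry.

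Second, the SAP does not say outright whether the primary test compares post-intervention means or changes. Its remark about allowing for baseline differences, and its description of the secondary outcomes as changes, lean towards a baseline-referenced contrast. Under that contrast the SAP's reason would also reach the strata, at least where their effect is constant over time, and the gain would be negligible. The reservation is fair. But the sentence that defines the test refers to the means of each arm at each time, and on its face that is a comparison where the strata matter.

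Third, R² is assumed throughout. Everyone enrolled must have at least moderate pain and a PEG average of 4 or more, which may narrow the spread between strata. The closed-form losses are also somewhat larger than those from the simulated mixed model, which lie closer to the SAP's analysis. Both points stand: the mixed-model range, about 0 to 3 points with balance and 0 to 4 without, is the better guide.

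None of this supplies a reason for omitting the strata, and the SAP gives none.

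**Conclusion.** The concern holds. The plan stratifies on two factors and specifies no analysis that includes either, and its stated reason does not cover them. The consequence is modest: no bias, no inflated type I error and no shortfall against the planned power.

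For an assumed R² of 0 to 15%, and a test of arm means at post-intervention, the power forgone is about 0 to 4 points with balance within strata and 0 to 5 points without it. Under balance the standard error is overstated by about 1.5 to 2, 3 to 4 and 5 to 6.5% at R² = 5, 10 and 15%, and the type I error is about 4 to 5%.

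These sizes rest on the assumed R², random dropout of 25%, two-sided 5% alpha and no therapy-group clustering. Under a change contrast with time-constant stratum effects the gain is close to nil. The change is worth making because it costs very little, not because the trial is at risk without it.

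**What to change.** Add long-term opioid therapy (yes/no) and chronic multisite pain (yes/no), as recorded at randomisation, as fixed effects in the primary and secondary mixed models and in the responder model. Add both to the imputation model in each arm. Stratum-by-time terms are not needed. Replace the statement that there are no covariates with, for example: *All models include the two randomisation strata as fixed effects; the baseline value of the outcome enters as the first repeated measure.* The SAP should also say whether the primary contrast is the post-intervention difference or the difference in change, since the gain depends on it. If the sponsor prefers no adjustment, it should give a reason that addresses the strata.

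The cost is a change of wording and two binary terms (2 degrees of freedom); both factors are already needed for randomisation. There are two caveats. The responder odds ratio becomes conditional on the strata. And the past tense in Endpoint and Covariates may mean that the models have already been run; changing the primary model then would be post hoc, and the stratum-adjusted model should be reported as a labelled sensitivity analysis.

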assumptions for these models using residual analysis including studentized residuals for individual observations, PRESS residuals which are composite residuals across an individual in longitudinal analysis, and Cook's distance. In compiling our analysis set, we will use an Intention to Treat (ITT) approach. We chose ITT for two reasons: 1) it fully exploits the benefits of balancing through randomization by including all patients who are randomized in the analysis; 2) it is a more "real-world" assessment of the intervention's impact as it allows for incomplete adherence and includes participants who may unintentionally cross over from the control to the intervention condition. Each of these issues can be handled well within the linear mixed models that will allow investigators to plot model-predicted trajectories for individuals with incomplete data. An additional advantage of linear mixed models is that they do not assume that the time between assessments is fixed and data for individuals who miss a time point can still be included. However, as this is the first efficacy trial to investigate STOMP, we will also conduct a per-protocol/as treated sensitivity analysis to understand the impact of the intervention without these complicating factors and adjust for differences by site. As a sensitivity analysis, missing data will be examined using multiple imputation methods. Specifically, multiple imputation using chained equations will be performed using previous baseline outcome data. Data will be imputed separately for each treatment group to improve efficiency and reduce bias in the treatment effect estimate.¹ Response to treatment defined by a reduction of at least 30% BPI Total score will be compared between groups using generalized linear mixed models with binary outcome using the same model effects and random components as the primary analysis.

Reference

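### The attrition check ignores arm, so it can miss opposite-direction dropout in the two arms and cannot tell harmless dropout from dropout that biases the contrast

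*Combined protocol and SAP*

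**What the plan says.** The SAP section Handling of Missing Values names two attrition diagnostics. In the first, "baseline characteristics will be compared between participants who do and do not withdraw from the study as a way to assess" the impact of attrition. The second reads: "We will also compare the rates of lost-to-follow-up (LTF) between study arms". It also commits to documenting reasons for missing data. No section of the protocol or SAP describes the participants who leave separately for each arm.

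The working assumption is stated as "Our general assumption will be that missing data is of the Missing at Random (MAR) mechanism". The primary analysis is a linear mixed model with baseline BPI-Total as one of the outcomes. On covariates, Endpoint and Covariates says: "There were no covariates included in our models, only time and treatment group indicator".

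The missing-data sensitivity analysis (Statistical Analyses) is by arm: "Data will be imputed separately for each treatment group to improve efficiency and reduce bias in the treatment effect estimate". Its predictors are limited, however: "multiple imputation using chained equations will be performed using previous baseline outcome data". Adjustment for site appears only alongside the per-protocol/as-treated sensitivity analysis. Long-term opioid therapy and multisite pain are randomization strata in the protocol, but they are not named in any model.

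On the expected amount of loss, the Sample Size Calculation says that, to reach a total divisible by 20 and "allow for 25% dropout (slightly more than in the pilot trial) we will recruit 280 participants".

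**The concern.** A treatment contrast is distorted when dropout leaves the two arms unlike each other on something that predicts the outcome. A comparison of all withdrawers with all non-withdrawers does not address that directly. If one type of participant leaves STOMP and the opposite type leaves usual care, the overall comparison cancels and the loss rates can be equal. If the same type leaves both arms, the overall comparison shows a strong difference although the contrast is unbiased, provided the treatment effect does not vary with that trait. The planned check can therefore be silent when there is a problem and loud when there is none.

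Different reasons for leaving are plausible here. STOMP participants are asked to attend 12 sessions, and they alone can receive transit vouchers (for sessions, not for outcome assessments). Usual care participants receive the manual, no additional treatment, and mid-study contact calls. At stake is whether the report could say that attrition had little impact on BPI-Total when the evidence for that statement was never collected in the right form.

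**Working it through.** **The plan's own figures.** The SAP states: "A sample size of 210 will provide 85% power to detect a difference of 1 on a 10 point scale with at standard deviation of" (the value given there is 2.4). With two-sided alpha of 0.05 assumed (not stated in the SAP), n per arm = 2 × (1.960 + 1.036)² × 2.4² / 1² = 103.4, so 104 per arm and 208 in all. With 105 per arm, power is 85.5% by the normal approximation and 85.2% by the exact t-test. Allowing for dropout, 210 / 0.75 = 280. These figures reproduce.

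**Inputs for the illustration.** From the documents: 140 per arm (280 at 1:1), 25% loss, SD 2.4. Assumed: 25% loss in each arm; a binary baseline trait held by 50%; a trait effect on follow-up BPI of 1.0 to 1.5 points beyond baseline BPI; baseline to follow-up correlation 0.5; no treatment effect; no therapy-group clustering.

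**Mirrored loss: 37.5% with the trait and 12.5% without it in STOMP, the reverse in usual care.**
- Loss rate in each arm: (37.5% + 12.5%) / 2 = 25%.
- Trait among withdrawers: 0.375 / 0.50 = 75% in STOMP, 25% in usual care; overall 50%.
- Trait among completers: 0.625 / 1.50 = 41.7% in STOMP, 58.3% in usual care; overall 50%.
- Size of bias = trait effect × 0.167, that is 0.17 points (effect 1.0) to 0.25 points (effect 1.5). Its direction depends on which arm loses the worse-prognosis type.
- Residual variance after baseline = 2.4² × 0.75 + effect² × 0.417 × 0.583 = 4.56 and 4.87. The standard error with 105 per arm = √(variance × 2/105) = 0.295 and 0.305. Bias / SE = 0.57 and 0.82, which gives type I error of about 9% and 13%.

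Simulation under these assumptions agrees: bias 0.17 to 0.25 and type I error 9 to 13%. The overall check is significant in 4 to 5% of trials and the loss-rate check in about 5%, both at chance. A by-arm comparison is significant in over 99%.

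**Milder mirrored loss, 33% against 17%.** Completers with the trait: 0.67 / 1.50 = 44.7% against 55.3%. Bias = 0.107 × effect = 0.11 to 0.16. The overall check flags about 5% of trials, the by-arm check about 87%. For a 30%/20% split the by-arm check itself has only about 48% power.

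**Selection in STOMP only: 37.5%/12.5% there, 25%/25% in usual care.** Completers with the trait: 41.7% against 50%. Bias = 0.083 × effect, about 0.08 to 0.12, with type I error of about 6 to 8%. Overall, the trait is held by (75% + 50%) / 2 = 62.5% of withdrawers and (41.7% + 50%) / 2 = 45.8% of completers, so the planned check can see it. It flags about 68 to 69% of trials, as does the by-arm check.

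**The same selection in both arms.** Completers with the trait: 41.7% in each arm, so bias is 0. The overall check flags 99.9% of trials.

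**Does the planned model remove the bias?** With a stronger mirrored split (40%/10%), a 1.2-point trait unrelated to baseline BPI and a true effect of −1.00, a likelihood estimate treating baseline BPI as an outcome gives −1.24, the same as completers alone. When the mirrored dropout depends on baseline BPI instead, completers give −1.31 but the likelihood estimate gives −0.99. The planned approach protects against dropout driven by BPI and not against dropout driven by a trait outside the model.

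**The case against.** The strongest reply is that the sharp contrast between the checks depends on exact mirroring. The check is blind only when opposite patterns nearly cancel, and the documents give no reason why usual care should lose the opposite type to the same degree. With selection in STOMP alone, splitting by arm gains no detection. A reader might infer that the planned check can never see different kinds of people leaving each arm; the STOMP-only case refutes that.

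A reader might also infer that any arm-different dropout biases the comparison. It does not: dropout driven by baseline BPI is handled by the mixed model, and the imputation is already done by arm. Its outcome-data predictors might extend to PHQ-8, which is a secondary outcome; the wording leaves this open. They would not include opioid therapy, multisite pain or site.

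The link from session burden to missing BPI data is weakened because, under Reminder calls, participants unwilling to attend sessions may be asked to complete outcome assessments only. The assumed trait effect equals or exceeds the target difference of 1; with exact mirroring and a 0.5-point trait, bias is about 0.09 and type I error 5.6%. Finally, the SAP does not say the arms are pooled. That is the plain reading of a sentence that does not mention arm, and it does not forbid a split.

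All of this stands and limits the point. What survives is that no stated analysis compares who leaves each arm, and that the overall check cannot separate harmless from harmful patterns.

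**Conclusion.** The point holds as a minor weakness in a supporting diagnostic. The planned check can miss opposite-direction attrition by arm, cannot distinguish it from attrition that is alike in both arms, and is not rescued by the loss-rate comparison. The exposure is confined to prognostic traits outside the mixed model and the imputation model.

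Its size ranges from about 0.08 to 0.12 points (STOMP-only selection) to 0.17 to 0.25 points (mirrored selection), against a target difference of 1. These figures rest on the assumed trait prevalence, trait effect, correlation and loss split, none of which the documents supply. A reader might go further and conclude that the primary estimate is biased. The documents do not support that: they contain no dropout data, and the calculation shows only what could go unseen.

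**What to change.** In the SAP section Handling of Missing Values, replace the overall comparison with a table of baseline characteristics for withdrawers and non-withdrawers within each arm. Report the arm-by-withdrawal contrast descriptively for a short prespecified list: long-term opioid therapy, multisite pain, site, PHQ-8 and baseline BPI-Total.

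Whatever the table shows, include the same non-BPI characteristics as predictors in the by-arm chained-equations sensitivity analysis, or as covariates in one sensitivity fit of the primary model. Do not select them by interaction tests: five independent tests at 5% give a 1 − 0.95⁵ = 23% chance of at least one false flag, have little power for mild patterns, and ignore whether the trait predicts BPI.

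The cost is one extra table and a slightly larger imputation model. Some arm differences will appear by chance, which is why they should be reported descriptively. The primary analysis is unchanged.

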A total of 280 participants who are patients at UAB and UNC - enrolled in CNICS, experiencing chronic pain (Brief Chronic Pain Screening Questionnaire (BCPQ) = at least moderate pain for at least 3 months) and moderately severe and impairing chronic pain (PEG pain questionnaire = average of all three times is 4 or greater).

Inclusion Criteria

1. Enrolled in CNICS
2. Age \geq 18 years
3. English-speaking
4. Chronic pain (Brief Chronic Pain Screening Questionnaire (BCPQ) = at least moderate pain for at least 3 months)

5. Moderately severe and impairing chronic pain (PEG pain questionnaire = average of all three items is 4 or greater)
6. Ability and willingness to attend the group sessions at the date/time specified
7. No plans for major surgery during the study period that would interfere with study procedures.

Exclusion Criteria

1. Do not speak or understand English
2. Are planning a new pain treatment like surgery
3. Cannot attend the group sessions
4. Had previously participated in the pilot study (STOMP)
5. Unwilling to provide informed consent

We will rely heavily on active recruitment using patients identified as having chronic pain on the BCPQ and PEG on CNICS pain Patient Reported Outcome measures.

Additionally, participants will be recruited via word-of-mouth by clinic staff or providers, calls generated from flyer tear-offs and other advertisements placed in the clinic.

b) PRE-SCREENING (phone and then in-person)

Potential participants will be prescreened over the phone using our prescreening phone script once the participating site. A HIPAA waiver will be submitted with the initial submission. If the individual passes the telephone prescreen, he or she will be scheduled for an in-person pre-screening visit by a member of the STOMP recruitment team. The date and time of the pre-screening visit along with the participant contact information and

preferred method of contact will be recorded on the Prescreening Visit Appointment Form. Data from the pre-screening phone call and visit appointment forms will be transferred to a prescreening excel log for accurate tracking. About 48 hours prior to the in-person prescreen visit, a reminder call from the research staff will be made to remind the potential participant of the prescreening visit. If the research staff cannot locate the potential participant after three attempts, the staff will note an inactive status in the prescreening log.

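### The primary mixed model, read naturally, imposes one variance and one correlation on baseline and both follow-ups; this may misstate the standard error of the primary test

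*Combined protocol and SAP*

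**What the plan says.** The SAP's Endpoint and Covariates section puts baseline in the outcome vector instead of adjusting for it. Under Statistical Analyses the fixed effects are arm, time and their interaction, and the dependence structure is given as "Models will include random effects for participant and therapy group". No random slope, residual covariance, visit-specific variance or robust standard error is named. The times are baseline, immediately post-intervention (0 months) and 3 months. On the test itself the SAP says "The primary hypothesis will be tested using the least squared means of each group at each time", without stating whether this is a difference at follow-up or a difference in change.

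The protocol's inclusion criteria (III.a) require a PEG score whose "average of all three items is 4 or greater", and the Baseline Assessment text (III.c) has the screening questions repeated at that visit. No such floor applies at follow-up.

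The Sample Size Calculation gives a single SD, 2.4, taken from the pilot. It does not say whether this is a baseline, follow-up or change SD.

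**The concern.** A participant random intercept with one residual variance averages the variance over all visits in the model. Baseline scores come from people selected for high pain, while follow-up scores are free to spread downwards. If baseline is the less variable visit, including it pulls the common variance below the true follow-up variance. The follow-up difference then gets too small a standard error, too narrow a confidence interval and a false-positive rate above nominal. The common correlation is a second restriction: two follow-up visits 3 months apart may well correlate more with each other than either does with a selected, pre-treatment baseline.

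This bears on the single primary test. It also bears on the missing-data strategy, because the SAP relies on the mixed model to deal with data missing at random, and that argument assumes a reasonable covariance model.

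**Working it through.** **Inputs from the documents.** Difference 1, SD 2.4, 85% power, 210 evaluable, 25% dropout, 280 recruited, 1:1 allocation, PEG cut at 4, three visits. Two-sided alpha is not stated; 0.05 is assumed.

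**Inputs assumed.** Unselected PEG and BPI-Total are normal with SD 2.4 and mean μ of 4 to 6. The PEG-BPI correlation r is 0.70 to 0.85. The between-visit correlation ρ before selection is 0.4 to 0.7. Follow-up is related to PEG only through baseline BPI-Total. Data are complete and there is no therapy-group effect.

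**1. The plan's own figure.** The SAP states "A sample size of 210 will provide 85% power to detect a difference of 1 on a 10 point scale", "assuming a two-sample t-test with equal variance". Per arm, n = 2 × (1.960 + 1.036)² × 2.4² / 1² = 103.4, so 104, or 208 in total. At 105 per arm the t-test has 85.2% power, and 210 / 0.75 = 280. The figure reproduces. It concerns one time point, so the points below do not alter it.

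**2. Difference at follow-up.** With complete data and saturated arm-by-time means, the fitted common variance is the average of the visit variances. The ratio of model to true standard error is

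q = √[(σ₀² + 2σ_f²) / (3σ_f²)], and type I error = 2Φ(−1.96q).

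With follow-up SD fixed at 2.4:

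| Baseline SD | q | Type I error |
|---|---|---|
| 2.6 | 1.029 | 4.4% |
| 2.4 | 1.000 | 5.0% |
| 2.0 | 0.948 | 6.3% |
| 1.7 | 0.913 | 7.3% |
| 1.4 | 0.883 | 8.3% |

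**3. What baseline SD does the entry rule imply?** The cut is on PEG. With a = (4 − μ)/2.4 and λ = φ(a)/[1 − Φ(a)], selection removes a fraction k = λ(λ − a) of the PEG variance. In units of 2.4², V₀ = 1 − r²k at baseline and V_f = 1 − ρ²r²k at follow-up, so selection shrinks follow-up variance too, but by less.

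- Strongest case (μ = 4, r = 0.85, ρ = 0.4): k = 0.637, V₀ = 0.540, V_f = 0.926, q = √[(0.540/0.926 + 2)/3] = 0.928, type I error 6.9%.
- Weakest case (μ = 6, r = 0.70, ρ = 0.7): k = 0.419, V₀ = 0.794, V_f = 0.899, q = 0.980, type I error 5.5%.

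Capping PEG at 10 as well raises the strongest case to 7.1%.

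**4. Difference in change from baseline.** The model variance is now the average variance of the three pairwise visit differences:

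q = √{[2·Var(f − b) + Var(f₁ − f₂)] / [3·Var(f − b)]}.

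Under the same selection, Var(f − b) = V_f + V₀ − 2ρV₀ and Var(f₁ − f₂) = 2(1 − ρ). The strongest case gives 1.034 and 1.2, so q = 1.026 and type I error 4.4%. The weakest gives 0.582 and 0.6, so q = 1.005 and type I error 4.9%. Range restriction alone is slightly conservative here.

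**5. Unequal correlations, same contrast.** Let each follow-up correlate 0.5 with baseline and 0.7 with the other.

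- Equal SDs of 2.4: Var(f − b) = 2 × 5.76 × 0.5 = 5.76; Var(f₁ − f₂) = 2 × 5.76 × 0.3 = 3.456; q = √(14.976/17.28) = 0.931; type I error 6.8%.
- Baseline SD 1.7: Var(f − b) = 2.89 + 5.76 − 4.08 = 4.57; q = √(12.596/13.71) = 0.959; type I error 6.0%.

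With 0.5 against 0.6 before selection, and the selection of step 3 applied, the result is 5.4% to 5.6%.

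**6. Simulation** (REML random intercept, 140 per arm, 2,500 trials per scenario, Monte Carlo error about 0.4 points near 5%; correlations 0.5 with baseline and 0.7 between follow-ups unless stated). For the difference at follow-up, baseline SDs of 2.0, 1.7 and 1.4 gave 6.0%, 7.5% and 8.3% with complete data, and 6.6%, 8.5% and 10.0% with 25% random dropout. Equal SDs (all correlations 0.6) gave 4.1% and 4.8%. For the change contrast at baseline SD 1.7 and all correlations 0.6, the results were 4.9% and 4.8%.

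**The case against.** The strongest reply concerns the contrast. The SAP says the model's treatment effects allow for baseline differences between arms. With a separate baseline mean per arm, a raw follow-up difference does not do that, whereas a difference in change does. On that reading range restriction alone does not inflate the error. This stands, and it is why the conclusion is given for both contrasts. Other text favours the follow-up difference: the models are said to compare arms at each follow-up time, and the planning test is a two-sample t-test. The SAP does not settle the matter.

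The cut is on the three-item PEG, not the 11-item BPI-Total, and no visit-specific SD is given. This stands too. A smaller baseline SD is probable, not documented.

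A random intercept is the natural reading of the SAP but is not stated, and other residual structures are not excluded. This also stands; naming the structure is part of the remedy.

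Residual checks are planned and could reveal unequal variances. The SAP names no alternative covariance if they do, so any change would be made after seeing the data.

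A reader might infer that type I error certainly exceeds 5%, or that it reaches 8% or more. The documents support neither. Equal SDs give 5.0% and a larger baseline SD gives less. The 8.3% figure needs a baseline SD of 1.4 against 2.4 at follow-up, a sharper contrast than the PEG cut produces under the assumptions above.

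**Conclusion.** The point holds conditionally. On the natural reading, the primary model assumes a common variance and correlation that the entry rule makes doubtful.

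- **Difference at follow-up:** two-sided type I error about 5.5% to 7% under the assumed PEG selection, with complete data and no therapy-group effect. The simulations suggest that dropout would push it somewhat higher.
- **Difference in change:** about 4.4% to 4.9% from range restriction alone. It is about 5.5% to 7% if the follow-ups correlate more with each other than with baseline; that excess is a correlation effect and also arises with equal SDs.

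Every figure rests on assumed SDs and correlations, because the documents give only the one SD. The departure from 5% is modest, but it affects the primary test and can be avoided. Clustering within STOMP groups is a separate matter and was not part of this check.

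**What to change.** In Statistical Analyses, replace the participant random intercept with an unstructured within-participant covariance over baseline, 0 and 3 months. Keep the therapy-group random effect and use Kenward-Roger degrees of freedom. State the primary contrast exactly: the between-arm difference at 0 months, or the between-arm difference in change from baseline to 0 months. The covariance change corrects the standard error under either contrast.

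Visit-specific residual variances around a random intercept would be a partial alternative: they release the variances but still force equal covariances between visits.

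The cost is SAP wording and four more covariance parameters (six in place of two), which 280 participants can readily support. The sample size of 210 evaluable and 280 recruited is unchanged.
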